6.1.2 Instrumental Variable Analysis

We will also use instrumental variable analysis (IVA) methods to assess the sensitivity of our results to unmeasured confounders. IVA is an alternative method for reducing selection bias that addresses both the effects of unobservable characteristics and the issue of dual causality between the choice of a treatment and the health outcome⁸⁴⁻⁸⁶. IVA methodology uses an indirect attribute that is closely associated with the type of treatment a patient receives, recreating randomized treatment assignment from a trial. This type of analysis requires identifying at least one factor that significantly affects treatment choice but is unrelated to the health outcome. IVA can be used to measure treatment effects independent of selection bias, which helps inform broad policy decisions, but it is limited in guiding clinical decisions for specific population subgroups⁸⁷. We will initially consider physician specific prescribing preference, as measured in the KPNC pharmacy database, as the instrument⁸⁸. It is necessary to consider how the characteristics of patients vary with respect to the instrument used when interpreting results of an IVA⁸⁴. Our access to a rich amount of data will permit a thorough evaluation of the validity of our candidate instruments. If our selected instrument appears to be valid, and we find that IVA yields different results compared with PS analysis, we will have confirmed the likelihood of unmeasured confounding in our PS analysis. Given the extensive control for confounding using our clinical data, and the large sample sizes, we anticipate PS analysis and IVA to yield similar results. However, if IVA yields results that vary from PS results, and our instruments are reasonably valid, it suggests the presence of unmeasured confounders in our treatment comparisons in the PS and traditional analyses. Thus, it will inform in the interpretation of findings with respect to possible impact of unmeasured confounders.

6.2 Avoidance of bias

The most important strength of the proposed study is the existence of the unique KPNC region-wide universal peripartum depression screening program. Such a universal screening provides a rare opportunity to conduct a large scale (N= 88,000) population-based comparative effectiveness study of depression treatment on reducing fetal risk, while avoiding potential selection bias. Without such a screening program, a large percentage of pregnant women with depression (>50%) would not have been identified, since depression during pregnancy is

substantially under-recognized and under-diagnosed^{5, 14, 45}. Thus, relying solely on clinical diagnosis of depression would likely lead to self-selection bias.

Given that randomized clinical trials are not feasible for evaluating treatment effectiveness on reducing fetal risk due to ethical concerns about assigning women into a treatment group with potential fetal risk, the proposed two-stage prospective cohort study is likely one of the best alternatives to examine the comparative effectiveness of treating depression during pregnancy. In addition to significantly reducing self-selection bias, the results of universal screening will provide information on depression severity measured by PHQ-9 score for participants. This valuable information will allow us to control for not only depression (yes/no), but also depression severity (a continuous scale) at baseline. While the distribution of depression severity was comparable among treatment groups (Table 2), ability to control for confounding by indication in such a refined detail will substantially increase the validity of our findings. Such a refined control for baseline depression severity is not likely feasible in other settings without universal peripartum depression screening.

We have also implemented several analytic methods to address the issue of possible selection into various treatment groups including *propensity score* analysis for balancing unobserved factors among treatment group and *instrument variable* analysis for possible unmeasured confounders (see Analytic Methods).

Finally, the findings from this observational study based on real world clinical experience is more relevant and applicable to actual clinical practice compared to findings from much controlled settings with selected populations (RCTs).

6.2.1 Study population

The proposed study will include all pregnant KPNC members (a population-based study), thus their racial/ethnic distribution will be similar as shown in Table 4 and will closely represent the underlying population (including Medicaid/MediCal) in the service region of Northern California. The study cohorts are described above (see C.b.2. Choice of comparators).

6.2.2 Sample size and statistical power

We expect to measure primary exposures (depression and treatment), and outcomes of interest (PTD, LBW) in approximately 88,000 women (stage-one sample). Randomly sampling from the stage-one cohort, we expect to recruit 400 pregnant women from each cohort (see Figure 2). Given the lack of methods for power calculations for the semiparametric maximum likelihood estimator (SMLE) in our two-stage sampling scheme, we very conservatively present minimum detectable effect calculations assuming the second stage sample of 3,600, noting that the gains in precision and statistical power in utilizing the measurements in stage-one sample of 88,000 women will be significant. In a small simulation study described below, we examine efficiency gains of an ad-hoc two-stage relative hazard estimator currently under investigation, which is an alternative to the semiparametric maximum likelihood estimator, attractive in its simplicity. These results provide information on the efficiency gains that can be expected in our two-stage design with the maximum likelihood estimation; the maximum likelihood estimator will be more efficient than the ad-hoc. Given results of the preliminary simulation study, we also present below estimates of minimum detectable effects using the two-stage SMLE for most estimates (in brackets, assumptions described below). Power calculations are based on the likelihood ratio test in the context of a Cox proportional hazards regression analysis and a logistic regression analyses, as appropriate to the outcome^{89 90}.

Given previous experience^{3,91-93}, we expect negligible loss to follow-up (< 1%). Based on our experience with our study population⁹⁴, we expect a rate of PTD (gestational age < 37 weeks) ranging from 8% - 11% and LBW ranging from 5% to 10%.

Each primary contrast of interest in analyses addressing **Aims 1 through 3** can be characterized as a comparison of two groups of 400 women with respect to risk of study outcomes of interest (N=800). Minimum detectable hazard ratios for PTD range from 1.69 – 1.83 across the range in expected rate of PTD (Table 5). Minimum detectable odds ratios for LBW range from 1.67 to 2.05 across the range in expected event rate.

Relevant to **Aim 4** analyses of heterogeneity in the association between treatment/depression and PTD by psychiatric comorbidity status (yes/no with 50% of total stage 2 sample in each of the two groups), the minimum detectable hazard ratio for effect modification (interaction) was calculated, assuming a pairwise comparison of treatment effect (e.g. A vs. D) and the midpoint of the range in expected PTD rate (9.5%) [N for analyses = 1600]. The hazard ratio for effect modification is interpreted as the factor by which exposure to the effect modifier (comorbidity status = yes) increases the hazard ratio associated with treatment, over and above that in those unexposed to the effect modifier (comorbidity status = no). Using methods as outlined above, the minimum detectable hazard ratio for effect modification is 1.50, and similarly for analyses of LBW, the minimum detectable odds ratio for effect modification is 1.62 (two-sided test, $\alpha=.05$, power =.80). While this stratification analysis is an *a priori* aim of the study with relevant clinical implications, we will be conservative in interpretation of our findings due to increased number of comparisons from stratification by depression type, though the need to adjust for multiple comparisons remains controversial⁹⁵⁻⁹⁷.

Table 4. Comparison of Maternal Age and Race/Ethnicity for Newborns between KPNC and the General Population in the KPNC Service Regions

Characteristics	KPNC Births (%)	All births in the KPNC Service Regions (%)
Maternal age		
< 20	12	10
20-29	43	52
30+	45	38
Maternal race/ethnicity		
Asian	15	16
Black	10	10

Table 5. Minimum detectable hazard ratios (HR) for preterm delivery and minimum detectable odds ratios (OR) for low birthweight in a pair-wise comparison of depression exposure/treatment categories (N=800); two-sided test, significance level (α) = .05, power (1- β) =.80.

Preterm Delivery (HR)		Low Birthweight	
Rate = 8%	Rate = 11%	Rate = 5%	Rate = 10%

Efficiency increase resulting from two-stage study design: A preliminary simulation study has been conducted providing information on the expected efficiency gains of the two-stage SMLE, relative to an analysis of the stage-two subsample only. For our preliminary simulation study, we made a few simplifying assumptions. We assumed three depression status categories, none, depressed without treatment, depression with treatments, with population prevalence set at 70%, 25% and 5%, and outcome relative risks of 1.0 (ref), 2.0 and 3.0, respectively. We assumed one binary confounder with varying prevalence across depression categories and strength of association with outcome. The event incidence was assumed at 5% (among those unexposed to depression and confounder). The stage-one sample size was 88,000, with random selection of 400 in each of the three exposure categories. Across the scenarios considered relative efficiencies [i.e. Var(stage 2

MLE) / Var(SMLE)] ranged from 4 to 82, demonstrating substantial gains by utilizing exposure and outcome information in the full sample of 88,000.

As a very crude approximation to the impact of incorporating the exposure and outcome information on 88,000 women, we took an “effective sample size” approach, and assumed the worst case among the simulation scenarios considered, where the relative efficiency of the SMLE was approximately 4.0. Thus, rather than basing power calculations on the stage-two sample size of 800, we based them on 3200 (i.e. $4.0 * 800$; 1,600 in each cohort category). Under these assumptions, the minimum detectable PTD hazard ratios are significantly decreased, ranging from 1.32 to 1.38 (for PTD rate ranging from 8%-11%) in pair-wise comparisons of depression exposure/treatment categories of interest. Similarly, the minimum detectable LBW odds ratios range from 1.32 to 1.45 (for LBW rate ranging from 5% to 10%). In addition, taking the same approach to estimation of efficiency gains, the minimum detectable hazard ratio and odds ratio for effect modification by comorbidity status (yes vs. no) are 1.31 and 1.37 in analyses of PTD and LBW, respectively. We acknowledge that these estimates of gains in efficiency are based on results from a simulation study which did not reflect the complexities in analyses that this study will encounter (e.g. multiple confounders, both multicategory and continuous).

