2 STUDY OBJECTIVES

Specific Aims: Depression during pregnancy is prevalent with nearly one million pregnant women suffering from it in US annually. Depression, if UNTREATED, has been linked to adverse fetal outcomes including preterm delivery (PTD) and low birthweight (LBW). Currently, significant confusion exists about risks and benefits of treating depression during pregnancy. Due to ethical concerns of randomizing pregnant women into treatment regimens with potential fetal risks, observational studies are likely the best alternative to RCTs, and have the advantage of providing real-life evidence of risks/benefits of depression treatment. Based on an universal depression screening program, we propose to conduct a comparative effectiveness study with a *two-stage* prospective cohort design to determine if treating depression in pregnancy is effective in improving fetal outcomes, and which treatment has the best risk-benefit profile: pharmacotherapy, psychotherapy or a combination. The questions will be examined separately for two depression types, *depression only* and *depression with other psychiatric co-morbidities*, to elucidate possible differences in treatment effectiveness between the two groups. Four cohorts will be formed within each depression type: (A) "Antidepressant only": screen positive for depression and use only antidepressants during pregnancy; (B) "Psychotherapy only": screen positive and receive psychotherapy only; (C) "Combination therapy": screen positive and receive both antidepressants and psychotherapy; (D) "Untreated depression": screen positive and receive no treatment. We will also form a cohort (E) "No depression": screen negative and receive no treatment, for baseline comparison. Information on depression, treatment and PTD & LBW will be available for all 88,000 women (stage-one sample). To control for confounding, we will randomly select 400 women from each cohort (total 3,600) for a telephone interview to obtain detailed information on confounding factors. Information from both stages will allow efficient and valid estimates while controlling for confounders. The aims are:

- Aim 1.** Do women who receive treatment during pregnancy have a lower fetal risk than women with untreated depression? (Cohort A, B & C vs. Cohort D).
- Aim 2.** Which treatment is more effective in reducing fetal risk? (Pair-wise comparison among Cohort A, B & C, respectively)

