Point and interval estimates of the relative hazard of PTD associated with each treatment modality (A, B, C), relative to no treatment (D) will be calculated via semiparametric maximum likelihood estimates of Cox proportional hazards regression parameters, with adjustment for potential confounders, as described above. In determining potential confounders in our regression models, we will first examine risk factors that may be plausibly linked to depression and PTD. Inclusion of potential confounding factors in our final regression models will be evaluated based on comparison of adjusted and unadjusted relative hazard ratios⁷⁹. Departures from model assumptions will be assessed via diagnostic plots of weighted residuals and tests for interaction between exposure and time (gestational age). The assessment of confounding variables for inclusion in regression models and testing of model assumptions will be performed in the stage-two sample using standard software for fitting Cox regression models. After determining the appropriate set of confounders and that there are no departures from model assumptions, the stage-one information on primary exposure and outcome will be incorporated using the semiparametric maximum likelihood estimator. This process applies to analyses of the remaining aims.

These comparisons will allow us to assess possible treatment effects on reducing PTD through both pharmacotherapy and psychotherapy. When compared to untreated (Cohort D), the comparison will be made after controlling for underlying severity of depression as measured by PHQ-9 scores or clinical diagnosis of severity before treatment. Table 2 shows that depression severity is relatively comparable among comparison groups, allowing control for confounding by indication (underlying depression severity, a unique strength of the proposed study due to the availability of PHQ-9 scores through the universal depression screening).

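### One set of detectable hazard ratios above 1 serves Aims 1 to 3, but Aim 1 looks for a lower risk than in Cohort D, and the plan gives neither a rate for D nor a detectable ratio below 1

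*Combined protocol and SAP*

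**What the plan says.** Section 6.2.2 treats each primary contrast under Aims 1 to 3 as "a comparison of two groups of 400 women with respect to risk of study outcomes of interest (N=800"). For all of them it gives one result: "Minimum detectable hazard ratios for PTD range from 1.69" to 1.83 across the expected PTD rates. The Table 5 caption sets the error rates: "two-sided test, significance level (α) = .05, power (1- β) =.80". The expected rates, 8-11% for PTD and 5-10% for LBW, come from experience with the study population and are not assigned to a cohort.

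Under the paragraph on efficiency from the two-stage design, a relative efficiency of 4 raises the effective size to "1,600 in each cohort category", and "the minimum detectable PTD hazard ratios are significantly decreased, ranging from 1.32 to 1.38". The LBW odds ratios are 1.67-2.05 at N=800 and 1.32-1.45 at N=3,200.

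Aim 1 (section 2) asks: "Do women who receive treatment during pregnancy have a lower fetal risk than women with untreated depression"? In section 6.1 the Aim 1 hazard ratios for each treatment, "relative to no treatment (D) will be calculated via semiparametric maximum likelihood estimates", take Cohort D as the reference. No detectable effect below 1 appears anywhere.

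**The concern.** At a fixed reference-group rate, a hazard ratio of 1/x produces fewer events than a hazard ratio of x, and power depends on events. A two-sided test gives both directions the same alpha but not the same power. A reader who takes 1.69-1.83 to mean that a benefit of 0.55-0.59 is also detectable with 80% power is making an assumption about the rate in Cohort D that the plan never states. Aim 1 is the leading question, and a null result will be judged against these figures.

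**Working it through.** **Inputs (section 6.2.2).** Two-sided alpha 0.05, power 0.80; n = 400 or 1,600 per group; PTD 8% or 11%; LBW 5% or 10%; likelihood ratio test. Loss to follow-up under 1% is ignored.

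**Step 1: reproduce the stated PTD figures.** Let p be the reference-group rate.

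- Likelihood ratio form: d0 = np, d1 = np·HR, m = (d0+d1)/2, λ = 2[d0 ln(d0/m) + d1 ln(d1/m)]. For 80% power λ must reach (1.960+0.842)² = 7.85. At n = 400, p = 0.08, HR = 1.83: d0 = 32, d1 = 58.56, m = 45.28, λ = 7.91. Solving for HR gives 1.83 (8%) and 1.69 (11%) at N=800, and 1.38 and 1.32 at N=3,200. All four match.
- Schoenfeld form: events E = np + n[1−(1−p)^HR], power = Φ(√(E/4)·|ln HR| − 1.96). This gives 1.82 and 1.69; 1.38 and 1.32.
- With 8-11% as the pooled rate, Schoenfeld gives 2.02 and 1.82; 1.42 and 1.35. These do not match.

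So the stated figures put 8-11% in the lower-risk group.

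**Step 2: turn the direction, with D as reference at 8-11%.** Detectable HR below 1:

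- N=800: 0.44-0.50 (Schoenfeld), 0.42-0.49 (likelihood ratio).
- N=3,200: 0.68-0.73 (Schoenfeld), 0.68-0.72 (likelihood ratio).

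Power at the reciprocals of the stated ratios (Schoenfeld):

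| n per group | Rate in D | Stated HR | Events | Reciprocal | Events | Power at reciprocal |
|---|---|---|---|---|---|---|
| 400 | 8% | 1.83 | 88.6 | 0.546 | 49.8 | 57% |
| 400 | 11% | 1.69 | 115.5 | 0.592 | 70.7 | 60% |
| 1,600 | 8% | 1.38 | 301.9 | 0.725 | 221.8 | 67% |
| 1,600 | 11% | 1.32 | 404.1 | 0.758 | 311.2 | 69% |

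**Step 3: the rate in D at which the reciprocals are right.** This is the rate the stated ratio implies in the higher-risk group, 1−(1−p)^HR.

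- N=800: 1−0.92^1.83 = 14.2%; 1−0.89^1.69 = 17.9%.
- N=3,200: 1−0.92^1.38 = 10.9%; 1−0.89^1.32 = 14.3%.

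**Step 4: a rate for D in line with the plan's premise (assumption).** Take 8-11% as the overall rate, 20% depressed (section 1) and relative risk 2 (the simulation's value for untreated depression), applied to all depressed women. Then overall = r(0.8 + 0.2×2) = 1.2r, and D = 2r = overall × 2/1.2, that is 13.3-18.3%. By Schoenfeld the detectable HR is 0.54-0.60 (0.75-0.78 with the factor of 4). Power at the reciprocals is 78.8% and 81.5% at N=800, and 87% and 89% at N=3,200. The likelihood ratio form runs one to two points lower.

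**Step 5: LBW, a separate matter.** Two-group binomial likelihood ratio: λ = 2n[k(p)+k(q)−2k((p+q)/2)], with k(a) = a ln a + (1−a) ln(1−a), solved for λ = 7.85 with q above p.

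| n per group | Reference rate p | q at 80% power | Odds ratio | Risk ratio | Stated OR | Power at stated OR |
|---|---|---|---|---|---|---|
| 400 | 5% | 10.2% | 2.16 | 2.04 | 2.05 | 73% |
| 400 | 10% | 16.7% | 1.81 | 1.67 | 1.67 | 67% |
| 1,600 | 5% | 7.4% | 1.51 | 1.48 | 1.45 | 70% |
| 1,600 | 10% | 13.2% | 1.36 | 1.32 | 1.32 | 70% |

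The N=800 values agree with risk ratios. At N=3,200 one of the two does.

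**The case against.** The strongest reply is that the plan does not place 8-11% in Cohort D. It ties the rate to the study population, in which the non-depressed Cohort E is the largest group, and its premise is that untreated depression raises risk: section 1 cites relative risks of 1.9-6.8 and the simulation uses 2.0. On that premise D is plausibly 13-18%, and Step 4 shows the reciprocals then have about 80% power or more. This stands. A reader might infer that 80% power fails for Aim 1; the documents do not support that, because it holds only if D has 8-11%. Nor do they settle it the other way. The simulation doubles a 5% baseline, which puts untreated women without the confounder at about 10%, inside 8-11%.

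A reader might also infer that ratios above 1 belong only to Aim 3. They do not. Section 1 raises possible harm from antidepressants, Aim 2 has no stated direction and the test is two-sided, so those figures remain relevant to every aim. The plan itself never labels them as harm; that follows from the values and the reproduced convention.

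Finally, the N=800 figures are described as very conservative, and the factor of 4 is the lowest of a simulated range of 4 to 82, so precision may be better than either set suggests. That is fair, but it does not supply a figure for Aim 1.

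**Conclusion.** The PTD arithmetic is correct for the convention used. The defect is that the reference-group rate is not tied to a cohort and the direction Aim 1 asks about is not shown. The detectable benefit runs from about 0.44-0.50 (0.68-0.73 with the factor of 4) if D has 8-11%, to about 0.54-0.60 (0.75-0.78) if D has 13-18%. The reciprocals of the stated ratios are valid when D is about 14-18% at N=800 and about 11-14% at N=3,200. The 13-18% rate rests on the assumptions in Step 4.

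The LBW odds ratios are a separate error. At 5-10% in the reference group they reach only 67-73% power in the direction above 1, so a shortfall at their reciprocals cannot be put down to direction alone. That they are risk ratios labelled as odds ratios is a likely explanation for N=800, not an established one.

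**What to change.** In section 6.2.2:

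1. State the PTD and LBW rate assumed in each reference cohort (D for Aim 1, E for Aim 3), with the reason for it.
2. Add detectable effects below 1 for Aim 1 at the stated D rate, by the plan's likelihood ratio method, for N=800 and N=3,200. Keep the existing hazard ratios above 1 for all aims.
3. Recalculate the LBW odds ratios. At 5-10% in the reference group, 80% power needs about 2.16-1.81 at N=800 and 1.51-1.36 at N=3,200, in place of 2.05-1.67 and 1.45-1.32.

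This changes text and table entries only; sample size and analysis stay as they are. The cost is that some stated figures become less favourable.

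### The stated low-birthweight detectable odds ratios have 67% to 73% power at two-sided 0.05, not the 80% claimed

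*Combined protocol and SAP*

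**What the plan says.** Section 6.2.2 (Sample size and statistical power) describes each primary contrast under Aims 1 to 3 as a "comparison of two groups of 400 women with respect to risk of study outcomes of interest (N=800"). It expects "LBW ranging from 5% to 10" per cent. On method it states: "Power calculations are based on the likelihood ratio test in the context of a Cox proportional hazards regression analysis and a logistic regression analyses", according to the outcome.

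For the single-stage calculation it reports: "Minimum detectable odds ratios for LBW range from 1.67 to 2.05 across the range in expected event rate". Table 5 covers both outcomes, and its caption reads in part "Minimum detectable hazard ratios (HR) for preterm delivery and minimum detectable odds ratios (OR) for low birthweight in a pair-wise comparison". The caption ends with the specification "two-sided test, significance level (α) = .05, power (1- β) =.80".

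The paragraph on the efficiency gain from the two-stage design multiplies the sample by 4.0, giving an effective "1,600 in each cohort category". On that basis "the minimum detectable LBW odds ratios range from 1.32 to 1.45 (for LBW rate ranging from 5% to 10" per cent). That paragraph announces no change of significance level, sidedness or power.

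**The concern.** The LBW figures look too small beside the PTD figures in the same section. With 400 per group, the detectable PTD hazard ratio at an 11% rate is given as 1.69, yet the detectable LBW odds ratio at a lower rate, 10%, is given as 1.67. With sample size, level and power fixed, a lower event rate makes the detectable ratio larger. For a given pair of risks, the odds ratio also lies further from 1 than the hazard ratio. Both effects should push the LBW value above 1.69.

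LBW is one of the two outcomes analysed under every aim. If the figures are wrong, the plan claims 80% power for effects it would miss in 27% to 33% of studies, and a null LBW result would be read as excluding effects that the study could not reliably detect.

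**Working it through.** **Inputs, all from section 6.2.2 and Table 5.** Two-sided α = 0.05; power 0.80; 400 per group (single-stage) or 1,600 per group (two-stage); LBW rate 5% to 10%; likelihood ratio test in logistic regression; loss to follow-up under 1%, ignored. The larger odds ratio is assigned to the lower rate.

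**Step 1. Find the rate convention from the PTD figures.** Take the stated rate p₁ as that of the reference group. Then p₂ = 1 − (1 − p₁)^HR, expected events d = (N/2)(p₁ + p₂), and power = Φ(½√d · ln HR − 1.96).

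| N | p₁ | Stated HR | p₂ | d | Power |
|---|---|---|---|---|---|
| 800 | 8% | 1.83 | 14.15% | 88.6 | 81.2% |
| 800 | 11% | 1.69 | 17.88% | 115.5 | 80.5% |
| 3,200 | 8% | 1.38 | 10.87% | 301.9 | 79.9% |
| 3,200 | 11% | 1.32 | 14.26% | 404.1 | 79.7% |

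All four PTD figures reproduce. If the rates are read as overall rates, power is only 68% to 74%. The plan's PTD figures therefore fit the reference-group reading.

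**Step 2. Apply the same convention to LBW.** The comparison-group rate is p₂ = p₁·OR / (1 − p₁ + p₁·OR). With p̄ the mean of the two rates and n the number per group, the likelihood ratio non-centrality is

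λ = 2n Σ [p ln(p/p̄) + (1 − p) ln((1 − p)/(1 − p̄))], summed over p₁ and p₂.

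Power is the probability that a non-central χ² on 1 df with parameter λ exceeds 3.841. Power of 80% needs λ = 7.85.

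| n per group | p₁ | Stated OR | p₂ | λ | Power at stated OR | OR with 80% power | n per group for 80% at stated OR |
|---|---|---|---|---|---|---|---|
| 400 | 5% | 2.05 | 9.74% | 6.69 | 73.4% | 2.158 | 477 |
| 400 | 10% | 1.67 | 15.65% | 5.75 | 67.0% | 1.805 | 549 |
| 1,600 | 5% | 1.45 | 7.09% | 6.18 | 70.1% | 1.514 | 2,040 |
| 1,600 | 10% | 1.32 | 12.79% | 6.18 | 70.1% | 1.365 | 2,034 |

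(The last column uses the pooled two-proportion formula.)

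A hand check of the second row with the pooled two-proportion test: the difference is 0.0565, the null standard error √(2 × 0.1283 × 0.8717/400) = 0.0236, and the standard error under the alternative 0.0236. Then (0.0565 − 1.96 × 0.0236)/0.0236 ≈ 0.43, and Φ(0.43) ≈ 0.67. The pooled test gives 72.8%, 66.7%, 69.9% and 70.0% for the four rows. Simulation with 200,000 data sets per row gives 73.7%, 67.5%, 70.3% and 70.2%.

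**Step 3. Try other readings of the LBW figures as odds ratios.**
- 5% and 10% as overall rates: power falls to 57% to 65%, and the odds ratios with 80% power become 2.59 and 1.96 (400 per group) and 1.58 and 1.39 (1,600 per group).
- The same odds ratios inverted, as protective effects: power falls to 46% to 60%.
- Wald, arcsine and unpooled tests in place of the likelihood ratio test: within about 1 point of Step 2.

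No variant reaches 80% at two-sided 0.05, and the reference-group reading is the most favourable to the plan.

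**Step 4. Look for a source.** Two-sided α = 0.10, which is one-sided 0.05, needs λ = 6.18 for 80% power. Both two-stage rows have λ = 6.18, and the detectable odds ratios are then 1.450 and 1.320, equal to the stated values. The same test at 400 per group gives 2.00 and 1.70, which do not match 2.05 and 1.67. The two-stage pair also fits two-sided 0.05 with 70% power.

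**Step 5. Check PTD against LBW without the LBW formula.** A hazard ratio of 1.69 at 11% gives p₂ = 17.88%, so the odds ratio is (0.1788/0.8212)/(0.11/0.89) = 1.76. At a 10% rate the detectable odds ratio should exceed that; the plan says 1.67. For the two-stage figures, a hazard ratio of 1.32 at 11% is an odds ratio of about 1.35; the plan says 1.32 at 10%.

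**The case against.** The strongest reply is that some of these values may be risk ratios labelled as odds ratios. At two-sided 0.05 and 80% power, the detectable risk ratio at 400 per group is 2.04 at 5% and 1.67 at 10%, against the stated 2.05 and 1.67. At 1,600 per group and 10% it is 1.317, against 1.32. Three of the four figures then fit, and for those three the fault would be the label. The comparison in Step 5 would also lose its force, because it depends on 1.67 being an odds ratio. This reading is possible but does not rescue the text. Section 6.2.2 and Table 5 call the LBW effects odds ratios throughout, the planned analysis is logistic, and 1.45 at 5% still fails (detectable risk ratio 1.476, power 76%).

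It is also fair to say that the one-sided match proves nothing about cause. It covers one pair only and has an equally good alternative. That stands: the conclusion here does not use it.

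The plan does not itself define the 5% to 10% as reference-group rates; that is inferred from the PTD figures. This also stands, but the other reading makes the shortfall larger.

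Finally, the plan calls the two-stage figures a crude approximation. They use the lowest relative efficiency from a simulated range of 4 to 82, so a move from 1.45 to 1.51 is small beside that uncertainty. This limits the practical weight of the two-stage correction. It does not apply to the single-stage figures, which the plan presents as conservative.

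**Conclusion.** The concern holds. As labelled, the four LBW odds ratios have 73%, 67%, 70% and 70% power, a shortfall of 7 to 13 percentage points against the stated 80%. The fault is specific to LBW, since the PTD figures in the same section reproduce.

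The conclusion assumes that the level, sidedness and power in Table 5 carry over to the two-stage paragraph, which restates none of them; that the rates are reference-group rates, the reading most favourable to the plan; and that the larger odds ratio belongs to the lower rate. The Table 5 cell values were not legible in the text available, so that pairing is inferred from the ranges in the prose.

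The cause cannot be settled from the documents. The single-stage pair fits risk ratios and the two-stage pair does not fully do so, so the two pairs appear to rest on different bases.

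**What to change.** Recompute both LBW pairs on one declared basis and correct section 6.2.2 and Table 5 together. For odds ratios with reference-group rates of 5% and 10%, a two-sided 0.05 test and 80% power:

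- 400 per group: replace 1.67 to 2.05 with 1.81 to 2.16.
- 1,600 effective per group: replace 1.32 to 1.45 with 1.37 to 1.51 (1.365 and 1.514 to three decimals).

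State beside the figures that the rates are reference-group rates and that the two-stage calculation uses the same two-sided 0.05 test and 80% power. If the sponsor intended risk ratios or overall rates, the text should say so and all four values should be recomputed on that basis.

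The cost is four figures and a sentence. The detectable effects become slightly less favourable; sample size, design and analysis are unchanged.
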